Those utilizing the Oculus Go HMD will be interacting with the VR game Ocean Rift. They will utilize a single controller to explore an underwater safari park. Ocean Rift has multiple environments to choose from, including coral reefs, ship wrecks, lagoons, the arctic, and prehistoric seas. Participants may interact with and learn about different creatures to include dolphins, turtles, orcas, ray, whales, sea lions, manatees, and dinosaurs. During the game users may travel where they please and interact with what they choose. The VR device is equipped with head-tracking software that allows the user to choose direction by looking around. The entire interior and exterior of the headset will be cleaned with alcohol-based wipes after each use. Alcohol will be used since it is generally well-tolerated on human skin, and since it evaporates quickly. The headset will be dried in the open air for a minimum of two minutes between each subject's use.

Those not using the VR will still wear a headset that will simply be turned off. This is to ensure that any significant change noted with the VR is due to the use of VR itself, and not simply due to "blindfolding" the patient during the procedure.

As some patients experiencing anxiety may be tempted to move during the procedure, lab personnel will instruct participants to remain still during venipuncture. Participants will be advised that they may take breaks as needed if anxiety becomes overwhelming.

After undergoing the procedure, each participant will be asked to fill out the post-procedure questionnaire and return it to the study team member present in the lab room, who will clean the headset as the participant completes the questionnaire. This questionnaire assesses the patient's pain intensity and level of anxiety with the VAS similar to the VAS shown above, as well as the patient's satisfaction with the visit which will be measured utilizing a Likert scale for individual questions (see below).

Overall, how satisfied were you with the use of Virtual Reality in reducing your pain level?

5 Very Satisfied	4 Satisfied	3 Not Sure	2 Unsatisfied	1 Very Unsatisfied
---------------------	----------------	---------------	------------------	-----------------------

Overall, how satisfied were you with the use of Virtual Reality in reducing your anxiety level?

5 Very Satisfied	4 Satisfied	3 Not Sure	2 Unsatisfied	1 Very Unsatisfied

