---------------------	----------------	---------------	------------------	-----------------------

How likely would you be to request Virtual Reality if it were available for use for other painful or anxiety-inducing procedures?

5 Very Likely	4 Likely	3 Not Sure	2 Unlikely	1 Very Unlikely
------------------	-------------	---------------	---------------	--------------------

10.2 Data Collection:

Describe all the data variables, information to be collected, the source of the data, and how the data will be operationally measured.

The independent variable for this study is the use of VR or lack thereof. The dependent variables include accurately measuring anxiety levels pre and post procedure, pain levels after the procedure, and satisfaction with the procedure in regards to pain control, anxiety management, and ease of use. The participant's gender, age, and a minimal medical history will be obtained for purposes of inclusion or exclusion from the study. The information collected relevant to the conduct of the study will include any history of bloodborne disease, anxiety, seizures, pregnancy status, right vs left handedness, VR experience, nausea, vomiting, or vertigo. Participants will also be asked to rate their expected pain and anxiety associated with venipuncture using the Visual Analog Scale (VAS). The above information will be collected on the self-reported data sheet prior to providing specimens. The questionnaires will also enquire as to whether the participant took any pain medications prior to arrival, as well as rate pre and post-procedure anxiety level on a VAS scale. Finally, patients will then rate their procedure related pain intensity on the VAS scale.

Participants will also be asked about their satisfaction level with the use of VR in regards to pain control, anxiety management, and ease of use and their likelihood of requesting VR if available in the future using the Likert scale. All information will be provided and data collected voluntarily, and participants may choose not to answer any questions they choose.

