Revised Common Rule, Section 219.116: General requirements for informed consent, whether written or oral, are set forth in this paragraph and apply to consent obtained in accordance with the requirements set forth in paragraphs (b) through (d) of this section. Broad consent may be obtained in lieu of informed consent obtained in accordance with paragraphs (b) and (c) of this

section only with respect to the storage, maintenance, and secondary research uses of identifiable private information and identifiable biospecimens.

Are you requesting a waiver or alteration of informed consent?

Yes No

Please explain the consent process:

The consent process will take place at the time of recruitment, and will occur in a private room with only the subject and investigator present. Participants will be walked through the informed consent document section by section, being allowed time to read each section and decide if they would like to continue. Participants will be informed prior to starting that participation is voluntary and that they may choose not to participate at any time during the consent process, throughout the duration of the study, and after it is complete. They will be informed on the process to withdraw from the study which will be to contact [name] at the above listed email or phone number which will be on the consent form and pointed out to the participant. Once complete the participant will be asked to sign the consent document and the PI will sign the consent form. Copies of the signed consent form will be made and provided to the participant. Participants will also be asked to fill out the Self-reported participant data form for inclusion /exclusion from the study and will be informed prior to leaving whether they are eligible to participate. All questions will be answered by the PI or AI at any point during participant contact or via email or phone.

13.5 DoDI 3216.02 requires an ombudsman to be present during recruitment briefings when research involves greater than minimal risk and recruitment of Service members occurs in a group setting. If applicable, you may nominate an individual to serve as the ombudsman.

N/A
 Propose ombudsman

13.6 Withdrawal from Study Participation:

Explain the process for withdrawal and specify whether or not the subjects will be given the opportunity to withdraw their data their data/specimens in the event they wish to withdraw from the study

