The decision to participate in this study is completely voluntary. No one will be coerced or intimidated into participating in this project. The principal investigator or his associate investigator will adequately answer any and all questions about this study, participation, and the procedures involved. If significant new findings develop during the course of this study that may relate to participant participation, they will be informed.

Subjects may withdraw this consent at any time and discontinue further participation in this study without affecting eligibility for care or any other benefits to which they are entitled. Should participants choose to withdraw, they must simply inform [name] that they have no desire to continue during their visit at the lab. As no PHI will be collected and subjects will be unidentifiable after completing questionnaires, participants will be unable to withdraw after completing all questionnaires.

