14.0 Risks and Benefits

14.1 Risks of Harm:

Identify all research-related risks of harm to which the subject will be exposed for each research procedure or intervention as a result of participation in this study. Consider the risks of breach of confidentiality, psychological, legal, social, and economic risks as well as physical risks. Do not describe risks from standard care procedures; only describe risks from procedures done for research purposes

Risk associated with this study may include dizziness, loss of awareness, eye strain, temporary visual abnormalities (including blurred or double-vision), muscle-twitching, impairment of hand-eye coordination, impaired balance, excessive sweating, drowsiness, fatigue, headache, lightheadedness, disorientation, nausea and/or vomiting from the use of the VR device, although the frequency of these events is rare not well-defined. Approximately 1 in 4,000 users may experience seizures despite having no history of seizure disorders; seizures are more common in children (who are excluded from this study). Risk of experiencing adverse events may be increased if patients have a history of seizure disorders, or if they have other underlying neurological disorders. Risk may also be increased if with the use of certain medications, although this data has not been studied.

There is also risk associated with accidental movement of arm during venipuncture, which could result in mistakenly puncturing unintended an area of the patients skin. However, this is unlikely as standard practice when drawing blood is for the phlebotomist to steady the patient's arm and draw skin taught with the hand not holding the needle, minimizing the likelihood that the patient will move.

There is also a risk in loss of subject confidentiality, which is addressed in section 14.2.

14.2

Measures to Minimize Risks of Harm (Precautions, safeguards):

For each research procedure or intervention, describe all measures to minimize and/or eliminate risk of harms to subjects and study personnel

Risks associated with the use of VR will be mitigated by screening for and excluding patients with a recent history of vertigo or dizziness, motion sickness, current symptoms of nausea and/or vomiting, and pregnancy. Additionally, in an effort to minimize risk, the following instructions will be provided during the tutorial:

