- If you begin to experience nausea, headache, eye strain, or any other discomfort, please remove the headset and inform a member of the research team immediately

Participants will also be advised to request breaks as needed if they experience uncontrollable anxiety, or they may withdraw if they request as stated in the consent form.

To minimize the risk of patients moving arms during venipuncture, phlebotomists will be asked to alert the patient that they are about to penetrate the skin and to hold still.

To minimize the risk of loss of confidentiality, all information collected will be controlled with strict record keeping procedures. All de-identified data collected will be stored in a locked drawer behind a locked door when not in use and only accessible to the research team members. Once gathered, the data will be transferred into electronic form on a secure CAC-enabled/password protected government computer that will be in the possession of the PI, when not in the PI's possession it will be stored in a locked room. The electronic documents will be kept for 3 years and then deleted. There will be no legal or economic risks associated with this study. No adverse action will be taken against anyone who withdrawals from the study at any time.

14.3

Confidentiality Protections (for research records, data and/or specimens):

Describe in detail the plan to maintain confidentiality of the research data, specimens, and records throughout the study and at its conclusion (e.g., destruction, long term storage, or banking). Explain the plan for securing the data (e.g., use of passwords, encryption, secure servers, firewalls, and other appropriate methods). If data will be shared electronically with other team members/collaborators outside the institution, describe the method of transmission and safeguards to maintain confidentiality. Explain whether this study may collect information that State or Federal law requires to be reported to other officials or ethically requires action, e.g., child or spouse abuse

All de-identified data collected will be stored in a locked drawer behind a locked door when not in use and only accessible to the research team members. Once gathered, the data will be transferred into electronic form on a secure CAC-enabled/password protected government computer that will be in the

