16.0 Reportable Events

16.1 Reportable Events: Consult with the research office at your institution to ensure requirements are met. Describe plans for reporting unexpected adverse events and unanticipated problems. Address how unexpected adverse events will be identified, who will report, how often adverse events and unanticipated problems will be reviewed to determine if any changes to the protocol or consent form are needed and the scale that will be used to grade the severity of the adverse event.

Consult with the research office at your institution to ensure requirements are met

- Describe plans for reporting expected adverse events. Identify what the expected adverse events will be for this study, describe the likelihood (frequency, severity, reversibility, short-term management and any long-term implications of each expected event)
- Describe plans for reporting unexpected adverse events and unanticipated problems. Address how unexpected adverse events will be identified, who will report, how often adverse events and unanticipated problems will be reviewed to determine if any changes to the research protocol or consent form are needed and the scale that will be used to grade the severity of the adverse event

Expected possible adverse events for this study are as follows:

Headache
Dizziness
Eye strain
Blurred vision
Muscle twitching
Eye strain
Disorientation
Excessive sweating
Loss of balance

The incidence of these events are not well-defined, so it's difficult to estimate the likelihood of these events occurring. However, participants will be instructed to discontinue the use of the headset if any of these symptoms, or any other discomfort occurs. If participants experience any of these symptoms and discontinue the use of the device, they will be monitored briefly by the research investigators as these symptoms should resolve spontaneously and should not have long-term implications. If symptoms do not resolve within 10-15 minutes, they will be escorted to the emergency room for further evaluation.

Expected adverse events will be reported by the principal investigator in the same fashion as unanticipated problems (stated below). As data collection is only expected to occur for 3-4 days, investigational staff will be reviewed after each adverse event to determine if changes need to be made to the research protocol or consent form.

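### Adverse-event capture is passive, with no symptom or early-removal item, so any symptom count is probably too low; late reports cannot be verified, and sections 13.4 and 13.6 conflict on withdrawal

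*Combined protocol and SAP*

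**What the plan says.** **How a symptom reaches the team.** In the tutorial, participants who feel unwell are told: "please remove the headset and inform a member of the research team immediately" (section 14.2). Section 16.1 likewise tells them to stop using the headset, and continues: "If participants experience any of these symptoms and discontinue the use of the device, they will be monitored briefly by the research investigators". A further step follows if symptoms have not settled in 10-15 minutes. Expected events are to be reported by the principal investigator.

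**What is recorded.** Of the post-procedure form, section 10.1 says: "This questionnaire assesses the patient's pain intensity and level of anxiety with the VAS". The form then adds satisfaction items. Section 10.2 describes the outcomes in the same terms: "The dependent variables include accurately measuring anxiety levels pre and post procedure, pain levels after the procedure", plus satisfaction. Neither section describes an item for symptoms during the study or for taking the headset off early. Section 11 contains no adverse-event summary.

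**What is expected.** Section 14.1 gives a long list of possible effects, including "impairment of hand-eye coordination, impaired balance, excessive sweating, drowsiness, fatigue, headache", and also nausea and vomiting. The list in section 16.1 is shorter. On frequency, section 16.1 says: "The incidence of these events are not well-defined".

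**After the visit.** Section 13.4 tells participants they may choose not to take part "throughout the duration of the study, and after it is complete", and gives email or phone as the route. Section 13.6 says "participants will be unable to withdraw after completing all questionnaires", because they can no longer be identified. Section 14.5 adds that the screening questionnaire is not linked to the consent form.

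**The concern.** Capture depends on the participant acting. Someone who feels dizzy or drowsy but finishes a short draw, or whose symptoms begin as the headset comes off, does not clearly meet the monitoring sentence in section 16.1, and no question described for the end of the visit would bring the symptom out. Participants are also told to keep still during the draw (sections 10.1 and 14.2), so some may sit through mild symptoms; that is an inference.

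Three things are at stake. First, the protocol says the frequency of these effects is poorly known and looks ahead to emergency and deployed use (sections 9.6 and 14.4), so a short or empty event list may be given more weight than it can bear. Second, a VR-arm participant who removes the headset before needle insertion stays in that arm under intention to treat, and no described field shows how often this happened. Third, participants are told two different things about withdrawing late. Data collection is expected to last only 3-4 days (section 16.1), so there is little time to correct the forms once it has begun.

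**Working it through.** **Design figure.** The plan gives no adverse-event rate or safety sample size, so the relevant stated figure is 30 per arm (section 11.4). It reproduces from section 11.5: n per arm = 2(1.96 + 0.842)² × (17/13)² = 26.8, rounded up to 27; 2 × 27 = 54; 54/0.90 = 60, or 30 per arm. The point below does not depend on this calculation.

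**Following a symptom through the text.**
1. Sections 14.2 and 16.1: the participant is told beforehand to stop and speak up.
2. Section 16.1: monitoring is written for a symptom together with discontinuation. The sentence on reporting expected events carries no such condition.
3. Section 10.1: the form is handed to a team member in the lab room. It covers pain, anxiety and satisfaction.
4. Section 10.2: no variable for symptoms, their onset or early removal is listed. The history of nausea, vomiting or vertigo is a screening item.
5. Section 16.1: the template asks how unexpected events will be identified and which severity scale will be used. The answer gives neither.

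**Symptom lists.** Section 14.1 includes nausea, vomiting, drowsiness, fatigue, lightheadedness, loss of awareness and impaired hand-eye coordination. None is in the section 16.1 list, which has eye strain twice. Section 17.1 names nausea as a side effect of VR systems.

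**Size of the under-count.** Neither the true rate p nor the captured fraction c is in the documents; the values below are assumptions. Apparent rate = p × c. Chance of recording no event in 30 = (1 − p × c)^30. Each cell gives the apparent rate and, in brackets, that chance.

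| True rate | c = 25% | c = 50% | c = 75% | c = 100% |
|---|---|---|---|---|
| 5% | 1.25% (69%) | 2.5% (47%) | 3.75% (32%) | 5% (21%) |
| 10% | 2.5% (47%) | 5% (21%) | 7.5% (10%) | 10% (4%) |
| 20% | 5% (21%) | 10% (4%) | 15% (1%) | 20% (0.1%) |
| 30% | 7.5% (10%) | 15% (1%) | 22.5% (<0.1%) | 30% (<0.1%) |

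**Limit with full capture.** With no events in N people, the one-sided 95% upper limit is 1 − 0.05^(1/N). For N = 30 this is 9.5%; for N = 60 it is 4.9%.

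**Exposure.** Everyone uses the working headset for about 5-10 minutes before drawing an envelope (section 10.1). A symptom in a control participant may therefore come from VR, and assigned arm alone does not define exposure.

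**Late contact.** Section 13.4 allows a participant to decline even after the study is complete, by email or phone. Section 13.6 has withdrawal stated during the lab visit and closes it once the questionnaires are done. With no described link from name to subject ID, a late request could not be carried out from the team's records.

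**The case against.** The other side has substantial points.

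- The sentence quoted from section 16.1 governs who is observed. The reporting sentence is not limited to those who stop, so the text does not show that the count is confined to them. Stopping is also what symptomatic participants are told to do, so symptom plus discontinuation is the expected sequence. This stands.
- A reader might infer that symptoms surface only when volunteered. A team member is in the room and receives the form, and section 16.1 has a separate response to seizure that needs no volunteered report. That inference is therefore too strong. However, the only tasks given to that team member are ensuring the assigned headset use, collecting the form and cleaning the headset; none is to ask about symptoms.
- A reader might infer that a later report can never be placed in an arm. Callers know whether their headset was on or off and can say so. What is lost is verification and linkage to the data record. Events during the visit can be tied to an arm through the subject ID and the allocation list.
- The team member ensures the assigned headset use, so early removal would be seen. It still has no described place to be recorded.
- An adverse-event rate is not a stated objective, and the limits above show that perfect capture would still give an imprecise rate. This stands, and it keeps the point in safety reporting.
- The withdrawal conflict concerns consent more than event capture, and section 13.4 does not expressly promise removal of data. The conflict remains.

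**Conclusion.** The point holds as a gap in safety data collection and a contradiction on withdrawal. As described, capture is passive and unprompted, so a symptom count would probably be too low by an unknown amount, and early headset removal in the VR arm would not be recorded. Under an assumed true rate of 10%, the chance of an empty record among 30 people rises from 4% with full capture to 10%, 21% or 47% at 75%, 50% or 25% capture. These figures illustrate the mechanism; they do not estimate this trial's event rate.

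The documents do not support reading this as a flaw in the efficacy result. The primary pain comparison is unaffected, and no adverse-event rate was promised.

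The conclusion rests on the forms as the protocol describes them. The data spreadsheet and the consent pages are not in the text available, the monitoring choice in section 15.1 cannot be read, and section 10.2 mentions an ease-of-use item missing from the questions displayed, so the actual form may hold more than is shown. The change is worth making because it is cheap, but the trial's main conclusion does not depend on it.

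**What to change.** 1. **Form.** Add to the existing post-procedure form, for both arms, a yes/no checklist of the symptoms in sections 14.1 and 16.1, with onset (tutorial or procedure) and severity, plus an item for early headset removal and its reason. Place these after the pain and anxiety VAS so that they cannot influence those ratings. Summarise by arm and by onset, since controls also use the working headset in the tutorial.
2. **Symptoms and monitoring.** Reconcile the lists in sections 14.1 and 16.1. Reconcile section 16.1 so that it states whether monitoring covers anyone reporting a symptom or only those who discontinue. Which rule applies is for the investigators and the IRB.
3. **Late contact.** Reconcile section 13.4 with section 13.6. One way is to give each participant a slip bearing only the subject ID, so that a later report or withdrawal can be linked without collecting PHI. This works only while the data file and the allocation list carry that number and are kept.

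**Cost.** About one minute per participant, one more form section, a paper slip and a few spreadsheet columns, with no extra staff. Prompted questions will raise the reported symptom rate in both arms, so the report should say that symptoms were solicited. The checklist removes the reliance on volunteering but cannot make the trial large enough for a precise rate.
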